1. RESEARCH QUESTIONS

1.1. OVERVIEW OF RESEARCH QUESTIONS

The primary overall research questions for this descriptive evaluation, which will be assessed utilizing pre- and post-surveys from nFORM, focus on program services and seeks to understand, "Is Strong Fathers, Stronger Families program participation associated with better participant outcomes?" This overall line of inquiry is operationalized by focusing on specific short-term outcomes to determine if parenting, co-parenting, and economic stability outcomes are improved after program participation.

No	Research Question	Implementation or Outcome?
11	Are participants offered primary workshops and support services as intended (fidelity)?	Implementation
12	How many primary workshops do participants attend (dosage), and how does this vary by workshop characteristics (e.g., timing and length of sessions) and participant characteristics (e.g., age, employment status, relationship status)?	Implementation
R1	Do SFSF-Midsouth participants experience significant increases in Co-parenting Relationship outcomes after program participation?	Primary Outcome
R2	Do SFSF-Midsouth participants experience significant increases in Parenting Relationship outcomes after program participation?	Primary Outcome
R3	Do SFSF-Midsouth participants experience significant increases in economic stability outcomes after program participation?	Primary Outcome

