1.2. OUTCOME RESEARCH QUESTIONS

For each outcome research question listed above, whether a descriptive or impact design, summarize the inputs (e.g., program components, program supports, implementation features, etc.), target population (e.g., the population for which the effect will be estimated) and the outcomes (e.g., child well-being, father-child engagement, etc.) that will be examined to answer the research question(s). Comparisons for descriptive evaluations may reflect circumstances before the grant, pre-treatment, or pre-determined benchmark from other studies with similar interventions.

Research Question Number Should correspond to the number indicated in Table 1.1 above	Intervention Program component or set of activities that the evaluation will test or examine	Target Population Population for which the effect of the treatment will be estimated	Comparison What the intervention will be compared to (e.g., pre-intervention for descriptive designs)	Outcome Changes that are expected to occur as a result of the intervention	Confirmatory or Exploratory? Confirmatory: those upon which conclusions will be drawn Exploratory: those that may provide additional suggestive evidence
R1	SFSF primary workshop curricula (40 hours)	Low-income, minority, young fathers (and father figures) in the Greater Memphis area	Pre- intervention	Improved co- parent relationships	Confirmatory
R2	SFSF primary workshop curricula (40 hours)	Low-income, minority, young fathers (and father figures) in the Greater Memphis area	Pre- intervention	Improved parenting relationships	Confirmatory
R3	SFSF primary workshop curricula	Low-income, minority, young fathers (and father figures) in the Greater Memphis area	Pre- intervention	Improved economic stability	Confirmatory

^{*} you may add rows by hitting the tab button, or right click and select insert row below

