9. DATA COLLECTION

9.1. CONSTRUCTS AND MEASURES

Clearly articulate the constructs of interest, measures to evaluate those constructs, and specific data collection instruments. Provide any information on the reliability and validity of the data collection instruments. For standardized instruments, you may provide the citation for the instrument.

^{*} you may add rows by hitting the tab button, or right click and select insert row below

Construct	Measure	Instrument	Reliability and Validity (if standardized instrument, you provide a citation for the instrument)
Program fidelity	Percent of enrolled participants who received each of the following: 1) primary workshops, 2) employment supports, 3) substantive service contacts, 4) referrals Number of substantive service contacts and referrals per participant	nFORM MIS	
Dosage	Number of primary workshop hours received, percent of target hours received Subgroup exploratory analysis of how dosage varies by workshop and participant characteristics	nFORM MIS	

Co-parenting Relationships	Composite measure that takes the average of 5 survey items related to positive co-parenting interactions with the mother of participant's youngest child (continuous, scale from 1-5 where 1 is strongly disagree and 5 is strongly agree). Improvement will be measured by a participant's change score, calculated by subtracting their pre-program composite score from their post-program composite score.	nFORM Community-Based Fathers Survey (A13: d-h)	Reliability and validity will be assessed with a correlation matrix and factor analysis
Parenting Relationships	Daily hours spent with youngest child in past 30 days (change score from preprogram to post-program) Frequency of reaching out to youngest child in past 30 days (change score from preprogram to post-program) Composite measure that takes the average of 10-11 survey items related to positive parenting behaviors with youngest child (continuous, scale from 1-5 where 1 is Never, 2 is 1 to 2 days per month, 3 is 3 or 4 days per month, 4 is 2 or 3 days per week, and 5 is every day or almost every day). Improvement will be measured by a participant's change score, calculated by subtracting their pre-program composite score from their post-program composite score.	nFORM Community-Based Fathers Survey (A2b, A2c, A5a-d: a-k)	Reliability and validity will be assessed with a correlation matrix and factor analysis

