Missing data for the implementation outcomes could happen as a result of programmatic data entry issues. For the sake of this evaluation, we assume that any primary or support services received by a participant are being accurately logged into nFORM, so a lack of documented attendance, service contacts, referrals, etc. is indicative of lack of services (i.e., a participant not receiving the program components as intended).

...

Assessing non-response bias

We will conduct response rate analysis for each primary outcome of interest to assess non-response bias and adjust for threats to internal validity. Using data from the Applicant Characteristics Survey, we will look at demographics (race, ethnicity, age, education level) and primary reason for joining the program among participants who fall into each of the following categories: 1) non-respondents who answered no surveys after the ACS, 2) respondents who completed the pre-survey only, 3) respondents who completed the post-survey only, and 4) respondents who completed both the pre-and post-survey (complete case).

Analytic approach

The main goal of this descriptive study is to assess pre-post change scores in the outcomes listed above among program participants before and after primary workshops. We will use paired sample t-tests to assess the magnitude and significance of changes among program participants in the analytic sample for each outcome. For binary economic stability outcomes, we will descriptively report the percent of participants who opened a checking or savings account during the course of the

program. We will adjust our p-values for multiple hypothesis testing and report the adjusted p-values in the appendix of the final report.

For the implementation analysis, program fidelity will be descriptively reported by the percentage of enrolled participants who receive: 1) any primary workshops, 2) employment supports, 3) substantive service contacts, 4) referrals. The program aims to provide all participants each of these four program components, so the percentage of participants who receive each of these will be compared to the 100% benchmark. Number of substantive service contacts per participant will also be compared to the benchmark of 8 SSCs set by OFA for FIRE grantees.

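### The SAP promises multiplicity-adjusted p-values but does not say that they decide the confirmatory conclusions for R1 to R3, and R2 has three tests with no rule for claiming improvement

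*SAP*

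**What the plan says.** - **Status of the questions.** Protocol section 1.2 marks R1, R2 and R3 as confirmatory, a label that its table defines thus: "Confirmatory: those upon which conclusions will be drawn".
- **Criterion.** Protocol section 1.1 frames all three in terms of significance. For R2 it asks: "Do SFSF-Midsouth participants experience significant increases in Parenting Relationship outcomes after program participation". Protocol section 5 then treats a significant pre-to-post improvement as the measure of the most benefit that could be credited to the services.
- **Tests.** SAP section 1, analytic approach: "We will use paired sample t-tests to assess the magnitude and significance of changes among program participants in the analytic sample for each outcome". The account-opening outcomes are not tested: "For binary economic stability outcomes, we will descriptively report the percent of participants who opened a checking or savings account".
- **Outcomes tested.** Protocol section 9.1 and the SAP's measure matrix give one for R1 ("Composite measure that takes the average of 5 survey items related to positive co-parenting interactions with the mother of participant's youngest child"). They give three for R2 ("Daily hours spent with youngest child in past 30 days", "Frequency of reaching out to youngest child in past 30 days" and the parenting-behaviour composite) and one for R3 (difficulty paying bills).
- **Multiplicity.** The SAP's statement is: "We will adjust our p-values for multiple hypothesis testing and report the adjusted p-values in the appendix of the final report". The documents give no significance level, sidedness, family or adjustment method. The only alpha in the SAP is the 0.7 threshold for item consistency.

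**The concern.** A multiplicity correction protects a conclusion only if the conclusion depends on it. The SAP accepts that a correction is needed and then leaves open whether adjusted or unadjusted p-values settle R1 to R3. The two can disagree when a raw p-value lies moderately below the threshold. With the method and family also unstated, the choice could be made after the results are known.

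R2 is the most exposed. It has three tested outcomes, and nothing says whether improvement in parenting relationships needs all of them, some of them, or is to be reported outcome by outcome. At stake is whether a reported significant improvement on a confirmatory question carries the error rate a reader would assume.

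**Working it through.** The documents give no family-wise error rate, so there is no figure to reproduce. The calculation shows what depends on the missing rule.

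**Inputs**
- Number of tests: 1 (R1) + 3 (R2) + 1 (R3) = 5, from Protocol 9.1 and the SAP. The two account outcomes are excluded because they are descriptive.
- Alpha per test: not stated. Two-sided 0.05 is assumed.
- Correlation between test statistics: not stated. A common value from 0 to 0.7 is shown.
- All error rates are computed with no true change in any outcome.

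**If unadjusted p-values decide**

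For independent tests, the chance of at least one false positive is 1 − (1 − α)^m.
- Five tests: 1 − 0.95^5 = 0.226.
- R2's three tests: 1 − 0.95^3 = 0.143.
- Five tests, false claims of improvement only (0.025 per test): 1 − 0.975^5 = 0.119.

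For correlated tests, 1,000,000 draws of five equally correlated normal statistics gave:

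| Correlation | Any false positive, five tests | False claim of improvement, five tests |
|---|---|---|
| 0 | 22.6% | 11.9% |
| 0.3 | 20.9% | 10.5% |
| 0.5 | 18.3% | 9.2% |
| 0.7 | 14.9% | 7.4% |

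R2's three tests alone give 12.6% at correlation 0.5. If only the R2 outcomes are correlated (0.5) and the rest are independent, the five-test figure is 21.1%.

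Sensitivity to the assumed alpha, five independent tests: 1 − 0.99^5 = 4.9% at 0.01, and 1 − 0.90^5 = 41.0% at 0.10.

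**If adjusted p-values decide (0.05)**
- Bonferroni, 0.01 per test, independent: 1 − 0.99^5 = 4.9%.
- Holm across five: 4.9% at correlation 0 and 4.2% at 0.5.
- Benjamini-Hochberg, with no true change anywhere: 5.0% and 4.5%.

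**Cost in power**

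The change detectable with 80% power, in SD units of the change score, is (z₁₋α/₂ + 0.842)/√n.
- α = 0.05: 1.960 + 0.842 = 2.802.
- α = 0.01 (strictest Holm step with five tests): 2.576 + 0.842 = 3.418.
- Ratio: 3.418/2.802 = 1.22, whatever the sample size.

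The SAP refers to Appendix B for the anticipated sample, and that figure is not in the text available. Both sample sizes below are therefore assumptions.
- n = 400: 2.802/20 = 0.140 SD rises to 3.418/20 = 0.171 SD.
- n = 1,347: 2.802/36.70 = 0.076 SD rises to 3.418/36.70 = 0.093 SD.

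**The case against.** A reader might infer that the adjusted values will appear nowhere but the appendix, that the main text will therefore judge significance on unadjusted tests, and that 18–23% is this plan's error rate. The documents do not support that. The SAP does not exclude other places for the adjusted values, and it does not say that unadjusted ones decide. A main-text conclusion can rest on values tabulated in an appendix. If the adjusted values do govern, the error is about 5% or less. This objection stands, and the figures are conditional for that reason.

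Four further objections:
- **Direction.** The questions concern improvement, so a false finding of worsening is not a false claim of benefit. This stands, and it roughly halves the five-test figures to 9–12%. That remains well above the 2.5% such a claim carries in a single test.
- **Family.** R1 and R3 have one test each, so 5% already holds for each of those questions. Treating all five as one family is a choice. This stands in part: R2 still has three tests.
- **R2.** Testing each outcome separately suggests outcome-by-outcome reporting, and no text says that one success in three is enough. That is a fair reading, but the plan does not state it, and the question is posed for parenting relationships as a whole.
- **Descriptive study.** The SAP template asks about Type I error where an impact analysis is proposed, and the protocol acknowledges that there is no counterfactual. That limits causal claims. It does not remove the multiplicity issue, because the protocol itself calls the questions confirmatory and frames them by significance.

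**Conclusion.** The point holds as a gap in the decision rule, not as proof that the conclusions will go uncorrected. The SAP commits to an adjustment but does not tie it to R1 to R3. Alpha, family and method are missing, and so is a rule for claiming R2.

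What turns on the gap, at an assumed two-sided 0.05 and common correlations from 0.5 down to 0:
- about 18–23% for at least one false positive across five unadjusted tests, against about 4–5% if Holm-adjusted values decide;
- about 9–12% if only false claims of improvement count;
- about 13–14% for R2's three tests alone, counting either direction.

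The rates are lower at higher correlation and change with alpha. This should be corrected. It does not call the design or the data collection into question.

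**What to change.** Replace the multiplicity sentence in the SAP's analytic approach with a short statement of:
1. the significance level and sidedness, for example two-sided 0.05;
2. the family and method, for example Holm across the five t-tested confirmatory outcomes, or at least across R2's three;
3. that the adjusted p-values decide the R1 to R3 conclusions and are shown beside the unadjusted values in the main results table;
4. that R2 is claimed only for the specific outcomes that pass, each named.

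The narrower option in item 2 controls error within each question but not across them. With R1, R2 and R3 each held at 5% and independent, the chance of at least one false positive overall is 1 − 0.95^3 = 14.3%. If that option is chosen, the SAP should say that control is per question.

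The change needs a few sentences and no new data. The price is slightly lower power per outcome, at worst the 1.22-fold rise in detectable change shown above. Later Holm steps are less strict, so the loss is usually smaller.
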